5.5.2.1. Follow-Up for Dose-Limiting Toxicities

Subjects whose treatment is discontinued due to a DLT must be followed until resolution or stabilization of the DLT event, whichever comes first.

5.6. Dose Adjustment of Study Drug

5.6.1. Planned Dose Increases

Cohort dose escalation is described in Section 4.1.1.

Intrasubject dose escalations of epacadostat are not permitted.

Intrasubject dose escalation of durvalumab to 10 mg/kg every 2 weeks will be allowed only for subjects who were enrolled into the study at a dose of durvalumab 3 mg/kg every 2 weeks, provided that the following criteria are met:

- The Protocol inclusion criteria are met.
- The subject has not experienced related or possibly related toxicity \geq Grade 2.
- The next dose level of epacadostat 25 mg BID and durvalumab 10 mg/kg has been determined to be safe based on DLT rules (eg, no DLTs during the DLT observation period).
- The subject is willing to submit to the PK [REDACTED] sampling schedule and durvalumab infusion observation as in Cycle 1.
- In the opinion of the investigator, the subject does not have any concurrent condition or circumstance that would complicate the dose escalation or PK sampling, or pose increased risk to the subject.
- The intrasubject dose escalation has been approved by the sponsor.

Note that if a subject dose escalates and experiences toxicity, guidance for dose interruption is provided in Sections 5.6.2 and 5.6.3. In cases of persistent toxicity, dose de-escalation may be considered if approved by the medical monitor.

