7.6.1.2. Pharmacokinetic Assessment for Durvalumab

Subjects will withhold morning dose of epacadostat on Cycle 1 Day 1 and Cycle 2 Day 1 before PK sample collection. Pharmacokinetic samples will be obtained in Phase 1 and Phase 2 of the study at the visits indicated in [Table 30](#). After the predose PK sample is drawn, subjects will take epacadostat and then begin infusion of durvalumab. The exact date and time of the PK blood draws will be recorded in the CRF along with the date and time of the last dose of study drug and last meal preceding the blood draw.

Measurement of durvalumab concentrations in serum will be performed using validated immunoassays. Only subjects who receive at least 1 dose of durvalumab and provide at least 1 post-treatment sample will be evaluated. Individual durvalumab will be tabulated by dose cohort along with descriptive statistics. The following PK parameters after the first and steady-state dose will be estimated (as data allow): C_{max} , C_{min} , t_{max} , and AUC. Accumulation to steady state will be assessed as the ratio of $C_{max,ss}:C_{max}$ and $C_{min,ss}:C_{min}$. All PK parameters will be estimated by noncompartmental analysis. Descriptive statistics of noncompartmental PK parameters will be provided.

Table 30: Sample Collection Windows for Pharmacokinetic Assessments for Durvalumab (Phase 1 and Phase 2)

Phase 1		
Study Visit	Timing of Sample Relative to Durvalumab Administration	
Cycle 1 Day 1 ^a	Predose	End of durvalumab infusion (± 10 min)
Cycle 2 Day 1	Predose	N/A
Cycle 5 Day 1		
Cycle 9 Day 1		
Cycle 13 Day 1	Predose	End of durvalumab infusion (± 10 min)
Every 4 cycles after Cycle 13	Predose	N/A
EOT	Anytime	
Safety Follow-Up Visit 2		
Phase 2		
Cycle 1 Day 1 ^a	Predose	End of durvalumab infusion (± 10 min)
Cycle 2 Day 1 ^a	Predose	N/A

^a Withhold the morning dose of epacadostat.

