### 3.1. Phase 1 Dose-Escalation Design

Phase 1 is the dose-escalation phase, which will include up to 7 cohorts of subjects treated with INCB024360 at doses of 25 mg twice daily (BID), 50 mg BID, 75 mg BID, 100 mg BID, 200 mg BID, and 300 mg BID in combination with MEDI4736 3mg/kg or 10 mg/kg given on Day 1 of each 14-day cycle.

A minimum of 3 subjects will be enrolled and treated in each cohort, and all 3 subjects will be observed for a minimum of 42 days before the subsequent cohort begins enrollment. In Phase 1, only 2 subjects may be enrolled within a week. A 1-week interval will be required between subjects in successive weeks.

Subjects must have received the cohort-specific dose of INCB024360 for at least 75% of the doses (63 doses) and have received at least 3 doses of MEDI4736 during the 42-day DLT observation period, or have reported a DLT to be evaluable for dose tolerability. Additional subjects will be enrolled in a cohort to achieve the minimum of 3 evaluable subjects if dropouts or dose interruptions/reductions occur that result in a subject being nonevaluable for DLTs. Alternative intermediate doses (eg, 75 mg once daily) or schedules (eg, 1 week on, 1 week off)

of INCB024360 may be evaluated based on emerging safety, PK, and PD observations. If an alternate schedule is tested and determined to be safe, re-escalation of INCB024360 according to [Table 1](#) will proceed.

The dose of INCB024360 will be escalated if 0 of the first 3 evaluable subjects enrolled report a DLT. If 1 of the first 3 evaluable subjects enrolled report a DLT, the cohort will be expanded to include 3 additional evaluable subjects. If 2 or more of either 3 or 6 subjects enrolled report a DLT, the prior dose level will be considered the MTD. If only 3 subjects were treated at this dose level, the dose will be confirmed as the MTD by evaluation of an additional 3 subjects before this dose is recommended for Phase 2 testing.

Alternative schedules of INCB024360 (ie, 25 mg BID 1 week on/1 week off) may be evaluated if 25 mg BID continuous treatment cannot be safely combined with MEDI4736 3 mg/kg. The cohorts and dose levels are shown in [Table 1](#). If cohort de-escalation is required and Cohort -1 is tested and determined to be safe, re-escalation of INCB024360 according to [Table 1](#) will proceed with the alternative treatment schedule of INCB024360. Intrasubject dose escalation is not permitted.

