#### **5.3.2. Phase 1 Safety Population**

The Phase 1 safety population includes all subjects enrolled in the Phase 1 portion of the study who received at least 1 dose of INCB024360 or MEDI4736. Treatment groups for this population will be determined according to the actual treatment the subject received on Day 1 regardless of the actual study drug the subject might receive during his/her continued participation in the study. All Phase 1 safety analyses will be conducted using the Phase 1 safety population.

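### Cohort 1 subjects may move from durvalumab 3 mg/kg to 10 mg/kg, but the SAP has no rule for their later data: AEs and first responses stay under 3 mg/kg, and accumulation ratios can mix two doses

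*Protocol*

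**What the plan says.** **Dosing.** Protocol 5.6.1 opens one route for a within-subject increase: "Intrasubject dose escalation of durvalumab to 10 mg/kg every 2 weeks will be allowed only for subjects who were enrolled into the study at a" starting level of 3 mg/kg, that is, Cohort 1 (epacadostat 25 mg BID). The conditions include that Cohort 2 has been judged safe on DLT rules, that "The subject has not experienced related or possibly related toxicity" of Grade 2 or higher, that the subject accepts PK sampling as in Cycle 1, and that "The intrasubject dose escalation has been approved by the sponsor".

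**SAP status.** SAP 2.1 bases the plan on Amendment 1 (29 SEP 2014) and keeps it in force for later amendments unless superseded. SAP Table 15 lists one version, 26 NOV 2014. The Protocol's amendment history shows that the escalation option came with Amendment 2 (20 FEB 2015). SAP 3.1 says "Intrasubject dose escalation is not permitted".

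**Grouping.** SAP 5.2 summarizes by the regimen first assigned. SAP 5.3.1 groups Phase 1 efficacy data by assignment at enrollment. SAP 5.3.2 groups Phase 1 safety data "according to the actual treatment the subject received on Day 1 regardless of the actual study drug the subject might receive" later. SAP 8.2.1 counts as treatment-emergent any AE that starts or worsens after the first dose, with no cut-off at a dose change.

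**PK.** Protocol 7.6.1.2 says "Individual durvalumab will be tabulated by dose cohort along with descriptive statistics" and "Accumulation to steady state will be assessed as the ratio of" Cmax,ss to Cmax and Cmin,ss to Cmin. SAP 7.5.1 repeats this. Neither document restricts the ratio to samples taken at one dose.

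**The concern.** Cohort 1 is the only cohort at durvalumab 3 mg/kg. If some of its subjects later receive 10 mg/kg, a table headed 3 mg/kg will contain toxicities and responses that first appeared at 10 mg/kg, and nothing in the table will tell the reader so. Safety and tolerability is the Phase 1 primary objective. ORR, durvalumab PK in combination and immunogenicity are secondary.

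The PK problem is separate. An accumulation ratio is meant to show build-up under a constant regimen. If the dose changes between denominator and numerator, the change of dose is read as build-up of drug.

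**Working it through.** The plan states no accumulation ratio, so there is no figure to reproduce. The check asks which samples can be affected and by how much.

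**1. Earliest escalation.** Protocol 4.1.1 requires 42 days of observation in Cohort 1 before Cohort 2 opens. Cohort 2 must then clear its own 42 days: 42 + 42 = 84 days, so Day 85 (Cycle 7 Day 1) at the very earliest. SAP 3.1 also limits Phase 1 entry to two subjects per week, which puts the third Cohort 2 subject about 7 days later: 84 + 7 = 91, so about Day 92. The next infusion on a 14-day schedule is Cycle 8, Day 1 + 7 × 14 = Day 99.

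**2. Samples at risk.** In Protocol Table 30 (Phase 1), end-of-infusion samples are scheduled at Cycle 1 and Cycle 13, and troughs at Cycles 2, 5, 9 and 13 and every 4 cycles thereafter. Cycle 5 is Day 57, before any escalation. Cycle 9 is Day 113 and Cycle 13 is Day 169, so both can follow it.

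**3. Size in one escalated subject.** The dose ratio is 10/3 = 3.33. Protocol 1.1.13.3.1 describes durvalumab AUC as approaching linearity from 3 mg/kg, so 3.33 is about the limit once steady state returns. The approach to it depends on half-life, which the documents do not give. Assume 10 to 26 days and a linear one-compartment model with 14-day dosing. With r = 2^(−14/half-life), h doses at 10 mg/kg and N doses in total before the sample, the ratio is inflated by

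1 + (7/3) × (1 − r^h) / (1 − r^N).

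Example: half-life 14 days (r = 0.5), escalation at Cycle 8. Cycle 13 peak: h = 6, N = 13, giving 1 + 2.333 × 0.9844/0.9999 = 3.30. Cycle 9 trough: h = 1, N = 8, giving 1 + 2.333 × 0.5/0.9961 = 2.17.

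| Escalation at | Cycle 9 trough | Cycle 13 peak | Cycle 13 trough |
|---|---|---|---|
| Cycle 7 | 2.29–3.00 | 3.18–3.33 | 3.11–3.33 |
| Cycle 8 | 1.77–2.45 | 3.10–3.33 | 2.99–3.32 |
| Cycle 10 | 1.0 | 2.82–3.29 | 2.59–3.21 |
| Cycle 14 | 1.0 | 1.0 | 1.0 |

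In the 14-day example, a subject whose Cycle 13 peak ratio would be 2.00 at a constant dose is reported as 6.59.

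**4. Size for the cohort.** With k of n contributing subjects escalated and back at steady state, the arithmetic mean is multiplied by 1 + (k/n)(10/3 − 1) and the geometric mean by (10/3)^(k/n). Protocol 4.1.1 and 9.2.1 give n = 3 to 6 evaluable subjects.

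| k of n | Arithmetic mean | Geometric mean |
|---|---|---|
| 0 of 3 or 6 | 1.00 | 1.00 |
| 1 of 6 | 1.39 | 1.22 |
| 1 of 3 | 1.78 | 1.49 |
| 3 of 6 | 2.17 | 1.83 |
| 2 of 3 | 2.56 | 2.23 |
| all | 3.33 | 3.33 |

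**5. Safety and response tables.** No arithmetic is needed. SAP 5.2, 5.3.1, 5.3.2 and 8.2.1 together place an event with onset after the first 10 mg/kg infusion in the 3 mg/kg column. ADA results follow by default, because SAP 5.2 presents tables by these groups unless otherwise indicated.

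**The case against.** Several points on the other side have force.

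- **The SAP sentence.** It closes a paragraph about INCB024360 schedules. Read for that drug alone, it agrees with Protocol 5.6.1, which also rules out epacadostat increases. That weakens the contradiction, but on either reading the SAP has no rule for a durvalumab increase.
- **PK handling is not fully specified.** Protocol 7.6.1.2 does not say whether a dose cohort means the initial or the current dose. Pharmacokineticists run these analyses (SAP 5.1) and may exclude subjects after reviewing dosing records (Protocol 9.1, SAP 5.3.5). Escalated subjects also give Cycle 1-type samples, so a 10 mg/kg denominator may exist. A careful analyst could avoid the error, but the text does not require it.
- **Grouping by assignment is a legitimate convention.** For response it is ordinary intention-to-treat practice, so the gap there is the missing flag. For safety, the Day 1 rule is explicit and hides the dose at onset in the tables, although the per-subject AE and dosing listings would allow it to be recovered.
- **Attribution.** Protocol 5.6.3 notes that immune-related AEs can appear months after the last dose. Onset after escalation does not show that 10 mg/kg was the cause.
- **Reach.** Only one small cohort is involved, and within it only subjects still treated at about 12 weeks or later who meet the conditions. The analyses are descriptive.

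A reader might infer that the cohort's ratio is inflated by at least 3.3-fold, or that every Phase 1 analysis is compromised. The documents support neither. The factor 3.33 is about the ceiling, and the cohort value is 1.0 if nobody escalates or if the steady-state samples come first. The 42-day DLT window (Protocol 5.5.1) closes before escalation is possible. SAP 6.4 computes the average durvalumab dose from recorded infusions. Cohort 1 does not enter the Phase 2 ORR.

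**Conclusion.** The point stands in limited form. The Protocol allows a durvalumab dose change for which the SAP, still in force, has no analysis rule. Followed as written, AEs and first responses with onset after the change are counted under 3 mg/kg without a flag, and accumulation ratios can combine a 10 mg/kg value at Cycle 13, possibly also at Cycle 9, with a 3 mg/kg first-dose value.

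The inflation is up to about 3.3-fold in an escalated subject and 1.0 to about 3.3-fold for the cohort mean. This rests on near-linear PK above 3 mg/kg, which the Protocol describes for AUC rather than for Cmax or Cmin, and on the assumed half-life range. A value slightly above 3.33 is possible only if exposure is still more than dose-proportional in that range. The number who escalated is not stated. The Amendment 3 rationale reports no DLTs in the first two cohorts, so the route could have been used.

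The change is worth making because it is cheap and because this is the only 3 mg/kg cohort. It does not bear on the 42-day DLT evaluation and MTD rule, or on the Phase 2 primary endpoint.

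**What to change.** 1. Reconcile SAP 3.1 with Protocol 5.6.1, stating which drug the SAP sentence covers. This is a request for consistency and takes no view on the dosing rule itself.
2. In Protocol 7.6.1.2 and SAP 7.5, define the dose cohort for durvalumab PK. Compute Cmax,ss:Cmax and Cmin,ss:Cmin only from samples at one durvalumab dose level, leaving post-escalation samples out of the 3 mg/kg ratio. If the Cycle 1-type samples at escalation serve as a new denominator, state how carry-over from 3 mg/kg is handled.
3. In SAP 5.2 and 5.3.2, keep the summary by initial assignment, and show AEs, ADA, PK and first responses with onset after the first 10 mg/kg infusion in a separate or flagged column. SAP 6.4 already treats re-treatment doses this way, first apart and then combined. Report the number escalated and the cycle of escalation, and note that onset date does not establish which dose caused an event.

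The cost is SAP wording, a matching sentence in the Protocol and one extra column. Dosing dates and sample times are already recorded. The price is fewer late samples at 3 mg/kg.

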5.6.2. Criteria and Procedures for Interruption or Dose Reduction

In some circumstances, it may be necessary to temporarily interrupt treatment as a result of adverse experiences that may have an unclear relationship to study drug.

Table 8 summarizes the dosing actions for epacadostat and durvalumab that must be implemented with the indicated related AEs. Additional information related to dose changes and AE management for irAEs can be found in Section 5.6.3.

In general, treatment with both study drugs should be withheld for \geq Grade 3 irAEs or non-irAEs and may be withheld for \geq Grade 2 irAEs. Additional details for irAEs are provided in Section 5.6.3.

If a criterion for dose reduction of epacadostat is met, refer to Table 9 to determine the appropriate dose for the subject. There will be no dose reductions of durvalumab allowed for the management of toxicities of individual subjects (exception noted in Section 5.6.1). Doses of

durvalumab may be delayed for toxicity management. In general, study treatment should be discontinued for toxicities that do not resolve to Grade 1 or less within 4 weeks of onset. Exceptions to this must be discussed with the medical monitor.

Note: There may be some circumstances where, due to toxicity attributed to epacadostat, a subject may not tolerate the combination therapy but may benefit from monotherapy with durvalumab. These cases must be discussed and approved by the medical monitor before the subject may receive durvalumab monotherapy on study.

Any interruptions of > 4 weeks or for LFT abnormalities must be discussed with the medical monitor prior to resuming treatment.

Except in cases of emergency, it is recommended that the investigator consult with the medical monitor (or other representative of the sponsor) before temporarily interrupting therapy for reasons other than Protocol-mandated medication hold. Additionally, the investigator must notify the sponsor's medical monitor and study project manager via email before restarting study drug that was interrupted for > 4 weeks due to an AE.

Table 8: Dose Modification Guidelines of Epacadostat and Durvalumab for Non-Immune-Related Adverse Events

Adverse Event	CTCAE v4.0 Grade	Action With Respect to Epacadostat	Action With Respect to Durvalumab
Non-irAE (first occurrence)	3	Hold study treatment until resolution to ≤ Grade 1 or baseline. ^a For AEs that downgrade to ≤ Grade 2 within 7 days or resolve to ≤ Grade 1 or baseline within 14 days, resume study treatment administration. Otherwise, discontinue study treatment.	Hold study treatment until resolution to ≤ Grade 1 or baseline. ^a For AEs that downgrade to ≤ Grade 2 within 7 days or resolve to ≤ Grade 1 or baseline within 14 days, resume study treatment administration. Otherwise, discontinue study treatment.
Non-irAE (second occurrence)	3	Hold study treatment until resolution to ≤ Grade 1 or baseline. ^a For AEs that downgrade to ≤ Grade 2 within 7 days or resolve to ≤ Grade 1 or baseline within 14 days, resume study treatment administration. Otherwise, discontinue study treatment.	Hold study treatment until resolution to ≤ Grade 1 or baseline. ^a For AEs that downgrade to ≤ Grade 2 within 7 days or resolve to ≤ Grade 1 or baseline within 14 days, resume study treatment administration. Otherwise, discontinue study treatment.
Non-irAE (third occurrence)	3	Discontinue epacadostat.	Hold study treatment until resolution to ≤ Grade 1 or baseline. ^a For AEs that downgrade to ≤ Grade 2 within 7 days or resolve to ≤ Grade 1 or baseline within 14 days, resume study treatment administration. Otherwise, discontinue study treatment.

Table 8: Dose Modification Guidelines of Epacadostat and Durvalumab for Non-Immune-Related Adverse Events (Continued)

Adverse Event	CTCAE v4.0 Grade	Action With Respect to Epacadostat	Action With Respect to Durvalumab
Non-irAE	4	Discontinue epacadostat.	Discontinue durvalumab.
Infusion-related reactions	1 or 2	Not applicable.	The infusion rate of durvalumab may be decreased by 50% or temporarily interrupted until resolution of the event. For Grade 2 infusion-related reactions, subsequent infusions may be given at 50% of the initial infusion rate. 
 • Acetaminophen and/or antihistamines may be administered per institutional standards at the discretion of the investigator. • Consider premedication prior to subsequent doses. • Steroids should not be used for routine premedication of \leq Grade 2 infusion reactions.
Infusion-related reactions	≥ 3	Discontinue epacadostat.	Discontinue durvalumab. Manage severe infusion-related reactions per institutional standards (eg, intramuscular epinephrine followed by IV diphenhydramine and ranitidine, and IV glucocorticoid).

^a If event is a laboratory AE without associated clinically significant signs or symptoms, as determined by the principal investigator, the subject may continue study treatment administration with approval from the medical monitor as long as steroid treatment has not been planned or initiated. Laboratory testing should be repeated within 72 hours. If the AE does not resolve to \leq Grade 1 in 7 days, the subject should then interrupt study treatment until event has resolved to \leq Grade 1 and restart at the next lower dose level.

Table 9: Dose Reductions for Epacadostat

Current Dose	Dose Reduction
25 mg BID	Discontinue epacadostat
50 mg BID	25 mg BID
75 mg BID	50 mg BID
100 mg BID	75 mg BID
300 mg BID	100 mg BID

5.6.3. Criteria for Subjects Exhibiting Immune-Related Adverse Events

This section is meant to apply to suspected irAEs from epacadostat, durvalumab, or the combination. Immune-related AEs may be predicted based on the nature of the durvalumab or epacadostat compounds, their mechanism of action, and reported experience with immunotherapies that have a similar mechanism of action. Special attention should be paid to AEs that may be suggestive of potential irAEs. An irAE can occur shortly after the first dose or several months after the last dose of treatment.

If an irAE is suspected, efforts should be made to rule out neoplastic, infectious, metabolic, toxin, or other etiologic causes prior to labeling an AE as an irAE. Subjects who develop a \geq Grade 2 irAE should be discussed immediately with the medical monitor.

Recommendations for management of specific immune-mediated AEs such as pneumonitis (see Section 5.6.3.1), enterocolitis (see Section 5.6.3.2), hepatitis (see Section 5.6.3.3), dermatitis (see Section 5.6.3.4), immune-mediated neuropathies (see Section 5.6.3.5), immune-mediated endocrinopathies (see Section 5.6.3.6), immune-mediated nephritis or renal dysfunction (see Section 5.6.3.7), and ocular manifestations (see Section 5.6.3.8) are detailed in the sections below.

General recommendations to managing irAEs not detailed elsewhere in this section are detailed in Section 5.6.3.12.

5.6.3.1. Procedures and Guidelines for Pneumonitis

Subjects with symptomatic pneumonitis should immediately stop receiving durvalumab and epacadostat and have an evaluation. Subjects should be monitored for signs and symptoms of pneumonitis or interstitial lung disease. The evaluation may include imaging (high resolution CT scan), bronchoscopy, and pulmonary function tests such as monitoring of oxygenation via pulse oximetry (resting and exertion) and laboratory work-up to rule out other causes such as infection. If the subject is determined to have study drug-associated pneumonitis, the suggested treatment plan is detailed in [Table 10](#).

Table 10: Recommended Approach for Handling Noninfectious Pneumonitis

Toxicity Grade	Withhold/Discontinue Durvalumab and Epacadostat	Guidance for Restarting Study Treatment	Supportive Care
Grade 1 (asymptomatic)	No action. Note: Consider holding study treatment as clinically appropriate during diagnostic work-up for other etiologies.	Not applicable.	For Grade 1 (radiographic changes only): 
 • Monitor and closely follow up in 2-4 days for clinical symptoms, pulse oximetry (resting and exertion), and laboratory work-up and then as clinically indicated. • Consider pulmonary and infectious disease consult.
Grade 2	Withhold epacadostat and durvalumab. Note: Permanently discontinue study treatment if upon rechallenge subject develops pneumonitis \geq Grade 2.	Hold treatment until resolution to \leq Grade 1 or baseline. 
 • If toxicity improves to \leq Grade 1 or baseline, then the decision to reinstate study treatment will be based on treating physician's clinical judgment and after completion of steroid taper. • If toxicity worsens, treat as Grade 3 or Grade 4. 	For Grade 2 (mild to moderate new symptoms): 
 • Monitor symptoms daily and consider hospitalization. • Promptly start systemic steroids (eg, prednisone 1-2 mg/kg per day PO or IV equivalent). • Reimaging as clinically indicated. • If no improvement within 3-5 days, additional work-up should be considered, and prompt treatment with IV methylprednisolone 2-4 mg/kg per day should be started. • If still no improvement within 3-5 days despite IV methylprednisone at 2-4 mg/kg per day, promptly start immunosuppressive therapy such as tumor necrosis factor inhibitors (eg, infliximab 5 mg/kg every 2 weeks). Caution: Important to rule out sepsis and refer to infliximab label for general guidance before using infliximab. • Once improving, gradually taper steroids over \geq 28 days and consider prophylactic antibiotics, antifungal or anti-PCP treatment (refer to current NCCN Guidelines for treatment of cancer-related infections [Category 2B recommendation]). • Consider pulmonary and infectious disease consult. • Consider discussing with medical monitor as necessary.

Table 10: Recommended Approach for Handling Noninfectious Pneumonitis (Continued)

Toxicity Grade	Withhold/Discontinue Durvalumab and Epacadostat	Guidance for Restarting Study Treatment	Supportive Care
Grade 3 and Grade 4	Discontinue epacadostat and durvalumab.	Not applicable.	
For Grade 3 or Grade 4 (severe or new symptoms, new/worsening hypoxia, life threatening):
 
 • Promptly initiate empiric IV methylprednisolone 1-4 mg/kg per day or equivalent. • Obtain pulmonary and infectious disease consult. • Hospitalize the subject. • Supportive care (oxygen, etc). • If no improvement within 3-5 days, additional work-up should be considered and prompt treatment with additional immunosuppressive therapy such as tumor necrosis factor inhibitors (eg, infliximab at 5 mg/kg every 2 weeks) started. Caution: Rule out sepsis and refer to infliximab label for general guidance before using infliximab. • Once improving, gradually taper steroids over ≥ 28 days and consider prophylactic antibiotics, antifungals, and, in particular, anti-PCP treatment (refer to current NCCN Guidelines for treatment of cancer-related infections [Category 2B recommendation]).

PCP = pneumocystis pneumonia.

